8.4.5 Reporting System for Serious Adverse Events

The reporting period for serious adverse events should begin when the subject signs the informed consent form and continue until 30 calendar days after the last use of the study medication (including the 30th day). If a serious adverse event occurs, both the initial report and follow-up reports should be made by completing theNew Drug Clinical Study Serious Adverse Event (SAE) Report Form, signing, and dating it, and then immediately reporting it by fax to the responsible research unit, the leading unit, the research unit's ethics committee, the National Medical Products Administration (NMPA, formerly CFDA), and the food and drug administration of the researcher's local area (province or city).

Serious adverse events occurring after the last administration of the drug within 30 days should generally not be reported unless they are suspected to be related to the study medication.

Serious adverse events should be detailed in terms of symptoms, severity, relevance to the trial medication, occurrence time, processing time, measures taken, follow-up time and method, and outcome. If the investigator believes that a serious adverse event is unrelated to the trial medication but potentially related to the research conditions (e.g., termination of original treatment, or comorbidities during the trial process), this relationship should be detailed in the narrative part of the serious adverse event page of the medical record report form. If the intensity of an ongoing serious adverse event or its relationship with the trial medication changes, the follow-up report of the serious adverse event should be immediately submitted to the sponsor. All serious adverse events should be followed up until resolution or stabilization.

Pre-existing Medical Conditions

Symptoms/signs present in subjects during the trial screening period should be recorded and reported as adverse events (AEs) only if there is an increase in severity, frequency, or nature after entering the trial (excluding the worsening of the disease under

study). Records should reflect changes relative to the previous state, such asincreased frequency of headaches.

Disease Progression

Disease progression is defined as a deterioration in the subject's condition caused by the primary tumor targeted by the investigational medication, with the appearance of new lesions related to the primary tumor or the progression of existing lesions considered as disease progression. Expected disease progression is not reported as an AE. Deaths, life-threatening conditions, hospitalizations or prolongation of hospital stays, permanent or severe disabilities/loss of abilities, congenital abnormalities/birth defects, and other significant medical events caused by expected disease progression symptoms and signs are not accelerated as serious adverse events (SAEs) for reporting.

New Anticancer Treatments

Within 90 days after the last administration, if a subject begins new anticancer treatments, only serious adverse events considered related to the study medication are recorded and reported.

8.5 Rapid Reporting of SAEs and Pregnancy

SAE Reporting:

The reporting period for SAEs is from the signing of the informed consent form to 90 days (inclusive) after the last administration of the medication. In the event of an SAE, whether it is the initial report or a follow-up report, the investigator must immediately complete the sponsor's Serious Adverse Event Report Form and report to the sponsor: [contact] within 24 hours of becoming aware of the event, and report to the national regulatory authority and ethics committee as required by Chinese regulations.

If a serious adverse event occurring outside the aforementioned period is determined to be related to the study medication, it should also be reported.

Investigators must report the completed SAE report form to the sponsor as soon as possible within 24 hours of becoming aware of the SAE. For deaths and life-threatening serious adverse events, investigators should urgently follow up on missing information and provide a complete SAE report. At the same time, investigators report to the national regulatory authority and ethics committee as required by regulations.

Pregnancy

Given the safety risk of embryotoxicity associated with similar drugs, all subjects of childbearing potential participating in the clinical trial must use effective contraceptive measures.

Should a female subject become pregnant during the clinical trial period when there is drug exposure, the subject will be withdrawn from the study. The investigator must report the pregnancy to the sponsor within 24 hours of becoming aware and complete theIntas Clinical Trial Pregnancy Report/Follow-up Form.

Should a male subject's partner become pregnant during the clinical trial period when there is drug exposure, the subject will continue in the clinical trial. The investigator must report the pregnancy to the sponsor within 24 hours of becoming aware and complete theIntas Clinical Trial Pregnancy Report/Follow-up Form.

The investigator must continuously monitor subjects who experience pregnancy and follow up on the outcomes of pregnancy, continuing follow-up until 8 weeks after the mother gives birth, and report the results to the sponsor.

If the pregnancy results in stillbirth, spontaneous abortion, fetal malformation (any congenital abnormality/birth defect), or medical abortion, it is considered a Serious Adverse Event (SAE) and must be reported following the SAE process and timelines.

If a subject experiences an SAE during pregnancy, it should be reported according to the SAE reporting procedures.

8.6 Events of Abnormal Liver Function

If AST and/or ALT levels are abnormally elevated in conjunction with a significant increase in total bilirubin levels, and there are no other causes of liver injury, it will be considered drug-induced liver injury. Such cases should always be regarded as significant medical events.

 Baseline
 Normal (AST/ALT and Total Bilirubin)
 Abnormal (AST/ALT and Total Bilirubin)

 Treatment
 ALT or AST ≥ 3× ULN with Total AST or ALT ≥ 8× ULN with Period
 Bilirubin ≥ 2× ULN and Alkaline an increase in Total Phosphatase ≤ 2× ULN and no hemolysis
 Bilirubin ≥ 1× ULN or a value ≥ 3× ULN

Table 12 Liver Function Injury Requiring Reporting as an SAE

Subjects should return to the research center for assessment as soon as possible after learning of the abnormal results (preferably within 48 hours). The assessment should include laboratory tests, a detailed medical history inquiry, and a physical evaluation, and the possibility of liver tumors (primary or secondary) should be considered.

In addition to repeating the testing of AST and ALT, the laboratory tests that should be conducted should also include albumin, creatine kinase, total bilirubin, direct bilirubin,

gamma-glutamyl transferase (γ-GT), prothrombin time/international normalized ratio, and alkaline phosphatase. A detailed medical history collection should include: history of alcohol consumption, acetaminophen, soft drugs, various supplements, traditional Chinese medicine, exposure to chemical agents, family medical history, occupational exposure, sexual history, travel history, contact with individuals with jaundice, surgeries, blood transfusions, history of liver disease or allergic diseases, heart disease, and immune disorders should be obtained. Further examinations may also include testing for acute hepatitis A, B, C, and E, liver imaging studies (such as biliary tract), autoantibody tests, and echocardiograms. If repeated tests confirm the laboratory criteria defined in Table 10, and there are no other causes for the abnormal liver function tests, the possibility of potential drug-induced liver injury should be considered without waiting for all the results of etiological tests for liver function abnormalities. Such potential cases of drug-induced liver injury should be reported as SAEs and aLiver Function Abnormality Monitoring and Follow-up Report Form should be submitted to the sponsor.

8.7 Management of Drug-Related Toxicity

The sponsor conducts regular safety audits at the trial level during the conduct of the trial. Detailed information including the frequency of audits and the types of data reviewed will be recorded in a separate trial-level safety audit plan.

8.7.1 Immune-Related Adverse Events

Given the mechanism of action of Sintilimab, which induces T-cell activation and proliferation, immune-related adverse events (irAEs) may be observed during this study. Signs and symptoms of irAEs in subjects should be monitored. If there is no clear alternative etiology (e.g., infection), signs or symptoms of diseases occurring during the trial in subjects should be considered related to the immune system.

Dose adjustments for Sintilimab and principles for adverse event management are detailed in Sections 5.2 and 5.3 of the protocol.

9 Statistical Analysis

9.1 Sample Size Calculation

Based on previous study data, the 1-year PFS rate for patients with extensive-stage small cell lung cancer (SCLC) receiving first-line chemotherapy does not exceed 5.4%. We estimate that the use of first-line Sintilimab combined with chemotherapy can increase the 1-year PFS rate of patients to 15%. Through sample size calculation, with α =0.05 (one-sided test), Power=80%, and assuming a dropout rate of 10%, using the One-Sample Logrank Test, a total of 45 patients need to be enrolled.

9.2 Statistical Analysis Plan

The statistical analysis endpoints for this study include:

Primary endpoint:

- To evaluate the 1-year PFS rate of subjects receiving first-line treatment with a PD-1 inhibitor combined with chemotherapy.

Secondary Endpoints:

- To evaluate the progression-free survival (PFS), overall survival (OS), and objective response rate (ORR) of subjects according to RECIST 1.1;
- To assess the quality of life of subjects based on the EORTC QLQ-C30 scoring;
- To evaluate the incidence of adverse events (AEs) in subjects.

Exploratory Endpoints:

- To identify potential predictive biomarkers of efficacy for immunotherapy in late-stage (extensive-stage) small cell lung cancer.

Statistical analysis will primarily utilize SPSS statistical software for programming and computation. Statistical tests will employ one-tailed and two-tailed tests; a P-value less than or equal to 0.05 will be considered to indicate a statistically significant difference, and confidence intervals will be reported at a 95% confidence level.

Patient Baseline Characteristics:

Calculate the mean, standard deviation, median, maximum, and minimum values for quantitative data such as age, height, and weight; list the frequency and percentage for qualitative data such as gender, ECOG score, etc.

Efficacy Analysis:

PFS and OS will be estimated using the Kaplan-Meier method to determine median values and their 95% CIs, and survival curves will be plotted. The objective response rate (ORR, which equals complete response [CR] plus partial response [PR]) and its 95% CI will be calculated. Quality of life scores will be compared with baseline values using paired t-tests or Wilcoxon signed-rank tests for within-group comparisons before and after treatment.

Safety Analysis:

Descriptive statistical analysis will primarily be used, with tables describing adverse events and adverse reactions (defined asadverse events 'definitely related/likely related/possibly

related' to the study drug) that occurred during the trial. Laboratory test results will describe conditions that were normal before the trial but abnormal after treatment, as well as the relationship between these changes and the study drug. Calculate the mean, standard deviation, median, minimum, and maximum values for vital signs and laboratory indicators before and after medication, using paired t-tests for before-and-after comparisons.

Compliance Analysis:

Summarize by group the proportion and frequency of subjects who violated the expected dosing regimen, the proportion of subjects whose study drug dosage was within 80% to 120% of the protocol-specified dose, and the proportion of subjects who completed the study and different treatment cycles.

10 Quality Assurance and Quality Control

Research personnel must be physicians who have received clinical trial training and work under the guidance of senior professionals.

Pre-trial inspections of clinical wards must meet standardized requirements to ensure that resuscitation equipment is complete.

It is recommended that professional nursing staff administer medication to subjects, understand in detail the medication intake, and ensure subject compliance.

Research centers must strictly follow the study protocol and accurately record case report forms.

Monitors should follow standard operating procedures, supervise the conduct of clinical trials, confirm that all data recording and reporting are correct and complete, all case report forms are entered correctly, and are consistent with the original data, ensuring that the trial is conducted in accordance with the clinical study protocol.

In the event of a Serious Adverse Event (SAE), it must be promptly reported to all research units, and if necessary, the study should be temporarily suspended.

11 Ethical, Regulatory, and Administrative Principles

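### The quality-of-life tests against baseline use a shrinking, progression-free set of patients across 15 domains at P ≤ 0.05, so apparent improvement can come from selective dropout and chance

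*Protocol*

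**What the plan says.** Section 9.2 of the protocol gives a general rule: "Statistical tests will employ one-tailed and two-tailed tests; a P-value less than or equal to 0.05" is taken as significant, and "confidence intervals will be reported at a 95% confidence level". It does not say which tests are one-tailed.

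For quality of life, section 9.2 states: "Quality of life scores will be compared with baseline values using paired t-tests or Wilcoxon signed-rank tests", as a within-group comparison before and after treatment. It gives no number of comparisons and no time point. The same section prescribes paired t-tests for vital signs and laboratory values.

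Section 7.3 describes 15 QLQ-C30 dimensions. They are collected on the first dosing day, at each imaging assessment and at the safety follow-up visit. Section 7.1.2 schedules imaging every 6 weeks, then optionally every 9 weeks after week 24. Imaging ends at progression, new anticancer treatment, withdrawal of consent or death.

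Section 9.1 sizes the trial for the 1-year PFS rate "with α =0.05 (one-sided test), Power=80"%, using a one-sample log-rank test and 45 patients.

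**The concern.** A paired test at a later scan needs a baseline score and a score at that scan. Because the questionnaire stops when imaging stops, patients who progress, switch treatment or die drop out of the comparison. The test then estimates the mean change among those still doing well, not the mean change in the treated group. If quality of life and progression are related, as one would expect in extensive-stage disease, the two means differ, and the bias favours improvement.

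The same threshold applies to every domain, with none nominated as the main one. A report could then claim improved quality of life that reflects who was left to answer and how many domains were tested.

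**Working it through.** **The plan's own figure.** Assume exponential PFS. The hazard ratio is ln(0.15)/ln(0.054) = 1.897/2.919 = 0.650. Events needed: (1.645 + 0.842)² / (ln 0.650)² = 33.3. Dividing by the 12-month event probability of 0.85 gives 39.2, so 40 patients. Then 40/0.9 = 44.4, so 45. The one-sided 5% design in section 9.1 reproduces.

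**Patients still under imaging.** Inputs: 45 patients and the planned 15% one-year rate (section 9.1); the scan schedule (section 7.1.2); constant hazard (assumption). The yearly hazard is −ln(0.15) = 1.897. Expected number progression-free at week w: 45 × exp(−1.897 × w/52.18).

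| Week | Expected progression-free of 45 |
|---|---|
| 6 | 36 |
| 12 | 29 |
| 24 | 19 |
| 51 | 7 |

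At the null rate of 5.4% (hazard 2.919) the counts at weeks 24 and 51 are about 12 and 3. Other dropout lowers all of these.

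**How large selective dropout could be.** The documents give no correlation between quality of life and staying on study, so this is an illustration over an assumed range. Suppose the true mean change is zero with standard deviation s, and the patients who stay are those with the better earlier change. Let that earlier change correlate ρ with the change at week 24. The fraction retained is p = 18.8/45 = 0.418, for which z = 0.208 and the normal density φ(z) = 0.390. The mean change among those retained is ρ·s·φ(z)/p = 0.935·ρ·s. With 19 patients this is a shift of 0.935 × ρ × √19 = 4.07ρ standard errors. The chance that a two-sided 5% test declares improvement is about 1 − Φ(1.96 − 4.07ρ); without selection it is 2.5%.

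- ρ = 0.1: shift 0.41, chance about 6%
- ρ = 0.3: shift 1.22, chance about 23%
- ρ = 0.5: shift 2.04, chance about 53%

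Simulated paired t-tests under the same assumptions agree to within about 1.5 percentage points.

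**Number of tests.** One before-and-after test per domain gives 15 tests. Expected false positives: 15 × 0.05 = 0.75. Chance of at least one, if independent: 1 − 0.95¹⁵ = 54%. Domains are correlated in practice, so 54% is a guide. Testing every domain at each first-year scan (weeks 6, 12, 18, 24, 33, 42, 51) gives 15 × 7 = 105 tests and 105 × 0.05 = 5.25 expected false positives. That is an upper reading for year 1, not something the protocol states.

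**Sidedness of the primary test.** With 80% power at one-sided 5%, power at two-sided 5% is Φ(1.645 + 0.842 − 1.96) = Φ(0.527) = 70%. At the planned effect, about one trial in ten would be significant one-tailed and not two-tailed, so the choice should be fixed in advance.

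**The case against.** *Quality of life is secondary in a 45-patient single-arm phase II trial, and multiplicity and missing data may be handled in a statistical analysis plan that is not shown.* This limits the weight of the point. It does not remove it, because section 9.2 itself names the test and the threshold.

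*The safety follow-up questionnaire captures patients who have just progressed.* True, and it partly offsets the selection. But it is one questionnaire about 30 days after the last dose. It falls at a different time for each patient and does not repair the comparisons made at scans.

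*The protocol plans 105 tests.* A reader might infer this from the collection schedule, but section 7.3 says when scores are collected, not when they are tested. Fifteen is the narrowest count.

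*Only survivors are analysed.* This is not exact. The set under imaging is progression-free, which is narrower than alive.

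*The rule in section 9.2 contradicts the one-sided design.* A reader might infer this too, but a one-tailed test at 0.05 is the design in section 9.1. A 95% interval beside it is ordinary reporting, and nothing makes the interval a decision rule. One can construct a conflict. With 6 of 45 progression-free, the exact one-sided P against 5.4% is 0.033, while the exact 95% lower limit is 5.05%. With 6 successes, checked from 38 to 45 patients, this happens only at 43 to 45; at 42 the lower limit is already 5.43%. At 6 of 45 it disappears with Wilson (6.26%), Jeffreys (5.76%) or log-log (5.414%) limits. The design test is also a one-sample log-rank, not an exact binomial. The example only illustrates why the roles of test and interval should be stated.

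**Conclusion.** The quality-of-life point holds as a worthwhile, inexpensive improvement. It follows from the protocol's own text that on-study paired comparisons rest on a set reduced to roughly 19 patients by week 24 and 7 by week 51. Those counts assume the 15% rate and a constant hazard. The direction of the bias follows if worsening patients leave earlier. Its size is not known from the documents: the 6% to 53% range depends entirely on the assumed correlation of 0.1 to 0.5. The 54% familywise figure assumes 15 independent tests.

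The sidedness of the primary test is a wording gap only. The protocol's sample size is not in question here, and its 95% interval is not wrong.

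**What to change.** In section 9.2, name one quality-of-life comparison: change from baseline in global health status at one early fixed scan. Week 6 or week 12 would leave about 36 or 29 patients progression-free on the assumptions above. Estimate it from a mixed model for repeated measures that uses all available scores together with baseline. State its missing-at-random assumption: the model corrects for dropout explained by scores already observed, not for dropout driven by scores never collected. Report the other 14 domains, and the laboratory and vital-sign comparisons, descriptively and without significance claims.

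In the same paragraph, state that the primary 1-year PFS test is one-sided at 0.05, that its matching interval is a two-sided 90% interval or a one-sided 95% bound, that the 95% interval is descriptive, and that all other tests are two-sided.

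The cost is a few sentences, slightly more analysis work and fewer significant secondary results. No extra patients or visits are needed.

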4.1 Inclusion Criteria

- (1) Age: ≥18 years and ≤75 years old;
- (2) A diagnosis of extensive-stage small cell lung cancer confirmed by pathology (including histology or cytology);

- (3) Previously untreated patients who have not received any systemic antitumor therapy;
- (4) Asymptomatic patients with brain metastases, or those with brain metastases that have been treated and have maintained a clinically stable condition for at least one month, and have not used steroids and anticonvulsant drugs for at least one month before entering the study:
- (5) Measurable lesions (according to RECIST 1.1 criteria, the longest diameter of the tumor lesion on CT scan is ≥10mm, the shortest diameter of the lymph node lesion on CT scan is ≥15mm, the scan slice thickness is no more than 5mm, and the measurable lesions have not received local treatments such as radiotherapy or cryotherapy);
- (6) ECOG PS: 0-2 points;
- (7) Expected survival of ≥3 months;
- (8) Adequate hematological function, defined as an absolute neutrophil count of ≥1.5×10^9/L, platelet count of ≥80×10^9/L, and hemoglobin ≥90g/L (no blood transfusion history within 7 days, and not corrected with G-CSF or other hematopoietic growth factors);
- (9) Adequate liver function, defined as a total bilirubin level ≤1.5 times the upper limit of normal (ULN) and aspartate aminotransferase (AST) and alanine aminotransferase (ALT) levels ≤2.5 times ULN for all patients;
- (10) Adequate renal function, defined as a creatinine clearance rate ≥50ml/min (Cockcroft-Gault formula):
- (11) Adequate coagulation function, defined as an international normalized ratio (INR) or prothrombin time (PT) ≤1.5 times ULN; if the subject is undergoing anticoagulant therapy, as long as INR/PT is within the range specified for the anticoagulant medication;
- (12) For female subjects of childbearing age, a negative urine or serum pregnancy test should be presented within 3 days before the first administration of the study drug. If the urine pregnancy test result cannot be confirmed as negative, a blood pregnancy test is required:
- (13) If there is a risk of conception, male and female patients must use effective contraception (i.e., a method with a failure rate of less than 1% per year) and continue to do so for at least 180 days after stopping the trial treatment; Note: If abstinence is the subject's usual lifestyle and the preferred method of contraception, then abstinence can be accepted as a contraceptive method;

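### Section 9.2 calls the safety analysis mainly descriptive, yet applies paired t-tests under a blanket P≤0.05 rule to about 34–42 laboratory and vital-sign variables, and its laboratory shift description leaves out patients abnormal at baseline (minor)

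*Protocol*

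**What the plan says.** The Safety Analysis paragraph of protocol section 9.2 opens with "Descriptive statistical analysis will primarily be used" and calls for tables of adverse events and adverse reactions. Two statements about laboratory data follow.

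- A shift description: "Laboratory test results will describe conditions that were normal before the trial but abnormal after treatment".
- Mean, standard deviation, median, minimum and maximum for "vital signs and laboratory indicators before and after medication, using paired t-tests for before-and-after comparisons".

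Earlier in the same section, two rules apply to all testing: "Statistical tests will employ one-tailed and two-tailed tests", and "a P-value less than or equal to 0.05 will be considered to indicate a statistically significant difference". Neither rule excludes the safety tests, and nothing says whether the safety tests are one- or two-sided.

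The synopsis (Statistical Methods) also calls safety evaluation mainly descriptive. It names no safety test.

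Eligibility (section 4.1) admits "aspartate aminotransferase (AST) and alanine aminotransferase (ALT) levels ≤2.5 times ULN for all patients", total bilirubin up to 1.5 times ULN, haemoglobin from 90 g/L and platelets from 80×10^9/L. Patients can therefore enter with abnormal laboratory values.

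**The concern.** There are three problems, all in text that the protocol itself fixes.

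1. **Chance labels.** A few dozen tests, each judged at 0.05, will mark some unaffected variables as significantly changed. Calling the analysis mainly descriptive does not remove a significance label that the same section attaches to every P-value.

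2. **Poor match to the safety question.** Laboratory toxicity often consists of a large change in a few patients. A paired t-test asks whether the average moved. A few extreme values raise the standard deviation along with the mean, so the test can stay silent.

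3. **A gap in the shift description.** As worded in 9.2 it follows patients from normal to abnormal. A patient who enters with ALT at twice ULN and worsens does not fit that description.

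At stake is how the laboratory section of the report reads. No endpoint or decision depends on these tests.

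**Working it through.** **The plan's own figure.** Section 9.2 gives no number for the safety tests. The sample size they rest on, "a total of 45 patients need to be enrolled" (section 9.1), can be reproduced from that section's inputs: 5.4% against 15%, one-sided α 0.05, power 80%, dropout 10%.

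- Hazard ratio = ln(0.15)/ln(0.054) = 0.650.
- Events = (1.645+0.842)²/(ln 0.650)² = 33.3.
- Patients = 33.3/0.85 = 39.2, rounded up to 40.
- With dropout: 40/0.90 = 44.4, rounded up to 45.

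So n = 45 is used below.

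**Number of variables.**

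- Long list. Note 6 to Table 1 has 10 blood count, 20 chemistry and 6 urine items = 36. Adding TSH (note 8) and 5 vital-sign values (note 3, blood pressure counted as two) gives 42.
- Short list. Table 10 has 6 + 18 + 5 = 29. Adding 5 vital-sign values gives 34.

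Both counts assume one before/after comparison per variable.

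**Chance findings if nothing truly changes.**

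- Expected number = 0.05 × m: 0.05 × 34 = 1.7 and 0.05 × 42 = 2.1.
- Probability of at least one, independent tests = 1 − 0.95^m: 0.825 (m = 34) and 0.884 (m = 42).
- Laboratory values are correlated. Simulating equally correlated normal statistics (two-sided, |z|>1.96) gives the following; the correlations are assumptions.

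| Correlation | m = 34 | m = 42 |
|---|---|---|
| 0.3 | 0.70 | 0.76 |
| 0.5 | 0.54 | 0.58 |
| 0.7 | 0.35 | 0.38 |
| 0.8 | not run | 0.28 |

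If some variables do change, only the rest count. As an illustration, if all 10 blood-count items on the long list shift, the expected number is 0.05 × 32 = 1.6.

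**Large rises in a few patients.** Suppose k of n patients rise by the same amount D and the rest change by exactly zero. Then:

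- mean = kD/n
- SD = D·√[k(n−k)/(n(n−1))]
- t = mean/(SD/√n) = √[k(n−1)/(n−k)]

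D cancels, so the size of the rise does not matter. With n = 45 (44 df; critical values 2.015 two-sided and 1.680 one-sided):

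| k | t | two-sided P | one-sided P |
|---|---|---|---|
| 1 | 1.000 | 0.323 | 0.161 |
| 2 | 1.431 | 0.160 | 0.080 |
| 3 | 1.773 | 0.083 | 0.042 |
| 4 | 2.072 | 0.044 | 0.022 |

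The zero-change condition is artificial. In a simulation with unit-SD noise in every patient and three of 45 raised by 10 SD, two-sided P≤0.05 occurred in 17% of runs with no drift. With a 0.3 SD drift in the same direction it occurred in 84%. The three severe cases are identical in both settings, so the label is decided mainly by the other patients.

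**Shift description against eligibility.** ALT, AST and bilirubin above ULN are allowed at entry, and these values are abnormal by the criterion's own terms. The 9.2 description starts from normal values. Worsening from an abnormal start is therefore outside that summary.

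**The case against.** The strongest reply is that little depends on these tests. They are not an endpoint, a gate or a stopping rule, and the section is labelled mainly descriptive. This stands, and it is why the point is minor.

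A reader might infer that severe toxicity in up to 3 of 45 patients can never reach significance. The documents do not support that. It needs a two-sided test and no change at all in everyone else, and 9.2 permits one-sided tests, for which 3 of 45 gives P=0.042.

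A reader might also infer that severe laboratory toxicity would go unreported, or that adverse-event incidence would be distorted. Neither follows. The sentence prescribing the t-tests also requires the minimum and maximum. Laboratory safety is graded by CTCAE v5.0 (note 10 to Table 1), and adverse events are tabulated separately. The synopsis speaks of abnormal laboratory changes without restricting them to patients normal at baseline. Section 8.6 sets a reporting threshold for patients whose liver tests are abnormal at baseline. The gap is confined to the 9.2 shift description.

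The false-positive figures assume no true change anywhere. That is generous for patients on chemotherapy: the dose rules in section 5.2.3 anticipate low platelets and neutrophils. The objection stands for the totals. It does not alter the 5% rate for each variable that is truly unaffected.

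One might read 9.2 as applying t-tests to graded dipstick results. The text does not say so, and this point does not rely on it.

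Finally, table layout and labelling often belong in a separate analysis plan. Here, though, the protocol itself names the test, the threshold and the scope of the shift description.

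**Conclusion.** The point holds as a minor one. Section 9.2 contradicts its own descriptive intent by placing about 34–42 paired t-tests under an unrestricted P≤0.05 rule. Each truly unchanged variable has about a 5% chance of being called changed. That means up to 1.7–2.1 such labels if none changes, and fewer if some do. The chance of at least one runs from about 0.28 (42 tests, correlation 0.8) to 0.884 (42 independent tests), depending on a correlation that the documents do not give.

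The tests are also a weak detector of rare large changes. With the other patients unchanged, 1 or 2 of 45 do not reach P≤0.05 on either sidedness, and 3 of 45 depends on which sidedness is used. Outside that idealised case, drift and noise in the other patients mainly decide the result.

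The shift description omits worsening from an abnormal baseline.

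**What to change.** In section 9.2, Safety Analysis:

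1. Delete the paired t-tests. If any before/after P-values are kept, state that they are descriptive and outside the P≤0.05 rule. Multiplicity adjustment is not the better remedy: Bonferroni would require P≤0.00147 (0.05/34) or P≤0.00119 (0.05/42), which makes the tests still less sensitive to changes in a few patients.
2. Replace the normal-to-abnormal description with a table, for each laboratory variable, of baseline CTCAE grade against worst on-treatment grade in all treated patients. Give the number, with exact 95% CI, who worsen by at least one grade and who reach grade 3–4.

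The cost is a few sentences and one standard set of tables. The data are already collected and CTCAE-graded. The only loss is the significance label on mean laboratory changes.
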